12.2. Description of statistical methods

Analysis will be undertaken according to a pre-specified statistical analysis plan.

Demographic and clinical data will be summarised with counts and percentages for categorical variables, means (standard deviations) for normally distributed continuous variables and medians (with interquartile or simple ranges) for other continuous variables.

Infants will be analysed in the groups to which they were randomly assigned, comparing the outcome of all infants allocated to intervention with all those allocated to the comparator group, regardless of deviation from the protocol or treatment received (referred to as the Intention to Treat (ITT) population).

The primary analysis will be adjusted for stratification factors (centre, infant's age at randomisation and mother's parity).

Binary outcomes will be analysed using risk ratios, whilst continuous outcomes will be analysed using either a mean or median difference as appropriate. 95% CIs will be presented for analyses of the primary and secondary outcomes.

Sensitivity analyses will be conducted on the primary outcome to investigate the impact of missing data, contamination and unmasking.

Pre-specified subgroup analyses will be undertaken, examining the primary outcome in the following groups:

- Infants aged less than two weeks vs. two weeks or older at randomisation
- Infants with BTAT score 4 or less vs. 5-6 vs. 7 or more at randomisation
- Prior belief concerning frenotomy: likely to be beneficial vs. uncertain vs. unlikely.

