6. OBJECTIVES AND OUTCOME MEASURES

Objectives	Outcome Measures	Time point(s) of evaluation of this outcome measure (if applicable)
Primary Objective To compare the rate of any breastfeeding at 3 months of age in infants with breastfeeding difficulties and diagnosed tonguetie who undergo frenotomy and receive breastfeeding support versus those who receive breastfeeding support only.	Any breastmilk feeding at 3 months according to maternal self-report: defined as any breastmilk feeding in the 24 hours prior to the infant reaching three months of age (Dennis, Jackson et al. 2014, McFadden, Gavine et al. 2017). A positive response is indicative of continuation of breastfeeding.	3 months of age
Secondary Objectives To investigate the effect of frenotomy on various important other secondary outcomes measured at first follow-up visit and/or three months of age. To investigate the impact of tonguetie severity and mothers' prior beliefs on the primary outcome.	Mother's breastfeeding self-efficacy: measured using the Breastfeeding Self- Efficacy Scale – Short Form Mother's pain while feeding during the previous 24 hours*: measured using visual analogue scale of the Short Form McGill Pain Questionnaire (SF-MPQ), modified into a Likert-type scale	First follow-up visit (outcomes indicated by *) 3 months of age (all secondary outcomes)
	Amount of breastfeeding support used: measured by total number of contacts (whether face to face or by telephone) with any breastfeeding supporter since the FROSTTIE procedure Infant weight gain: measured as difference in weight for age z-scores between birth and three months of age Infant post-randomisation weight gain: measured as difference in weight for age z-scores between baseline and three months of age	

Exclusive breastmilk feeding*: exclusive breastmilk feeding in the previous 24 hours

Exclusive direct breastfeeding*: exclusive breastfeeding directly from the breast with no bottle feeds of expressed milk in the previous 24 hours

Age of child when s/he last received breastmilk: age when child last received breastmilk, to determine when and whether switch to exclusive formula feeding has occurred

Time spent breastfeeding in previous 24 hours: time in minutes/hours spent breastfeeding in previous 24 hours

Frenotomy in comparator group*: measured by a specific question

Repeat frenotomy*: measured by a specific question

Bleeding following frenotomy or frenulum tear*: measured by a specific question

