8.2. Inclusion criteria

 Any infant aged less than 10 weeks referred (by parent or other breastfeeding support service) to an infant feeding service with breastfeeding difficulties and judged to have tongue-tie, whose parent has given informed consent for participation.

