9.4. Randomisation

The infants entered into the trial will be randomised 1:1 to either:

- frenotomy with standard breastfeeding support (intervention arm), or
- no frenotomy with standard breastfeeding support (comparator arm).

Multiples (twins or higher order multiples) will be randomised to the same arm. Stratified block randomisation (using variable block sizes) will be performed via a secure 24-hour web-based randomisation system (hosted by the NPEU CTU, University of Oxford) stratified by infant's age (<2 and ≥2 weeks) at randomisation, mother's parity (primiparous or multiparous) within centre. A telephone back-up system will be available 24 hours a day (365 days per year). Users of the system will have no insight into the next allocation.

A statistician independent of the trial at the NPEU CTU will generate the randomisation schedule and the Senior Trials Programmer will write the web-based randomisation program; both will be independently validated. The implementation of the randomisation procedure will be monitored by the Senior Trials Programmer and independent statistician throughout the trial and reports will be provided to the Data Monitoring Committee.

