9.5. Baseline assessments

Baseline information will be collected on sociodemographic and other characteristics, including:

- Infant birthweight
- Infant current weight
- Estimated date of delivery
- Current feeding practices (e.g. expressed breastfeeding, use of infant formula)
- Assessment of the degree of tongue-tie using the BTAT
- Mother's prior beliefs about frenotomy: Using a three-point Likert scale, the opinions of all
 mothers of infants recruited to the trial will be sought at the time of recruitment on their prior
 belief of the potential benefit of frenotomy
- EQ-5D-5L
- Mother's pain while feeding during the previous 24 hours: measured using visual analogue scale
 of the Short Form McGill Pain Questionnaire (SF-MPQ), modified into a Likert-type scale (scores
 ranging from 0 to 10) (Dennis, Jackson et al. 2014)
- Exclusive breastmilk feeding: exclusive breastmilk feeding in the previous 24 hours

• Exclusive direct breastfeeding: exclusive breastfeeding directly from the breast with no bottle feeds of expressed milk in the previous 24 hours

Pre-trial entry breastfeeding support received

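### The primary model omits feeding status at entry, which the trial already collects, and gives age no coding finer than a two-week split; adding both is a small gain in precision at almost no cost

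*Protocol*

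**What the plan says.** Section 12.2 fixes the covariates of the primary analysis: "The primary analysis will be adjusted for stratification factors", listed there as centre, the infant's age when randomised and the mother's parity. It names no others. Section 9.4 gives the coding used at randomisation: "stratified by infant's age (<2 and ≥2 weeks) at randomisation, mother's parity (primiparous or multiparous) within centre". Section 12.2 uses the same two-week cut for a subgroup analysis. Eligibility reaches well beyond that cut: "Any infant aged less than 10 weeks referred" (section 8.2).

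Section 9.5 lists what is recorded at baseline. It includes "Exclusive breastmilk feeding: exclusive breastmilk feeding in the previous 24 hours", and also current feeding practices, exclusive direct breastfeeding, pain on a 0 to 10 scale, EQ-5D-5L and current weight.

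For effect measures, section 12.2 says: "Binary outcomes will be analysed using risk ratios, whilst continuous outcomes will be analysed using either a mean or median difference as appropriate". It does not say whether the secondary comparisons are adjusted. Section 6 defines post-randomisation weight gain as a change score, "measured as difference in weight for age z-scores between baseline and three months of age". Section 12.2 refers the detail of the analysis to a pre-specified statistical analysis plan, which is not at hand.

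**The concern.** The primary outcome is any breastmilk feeding at 3 months. An infant already partly formula-fed at entry is plausibly more likely to have stopped by then than one fed only breastmilk. The protocol gives no figure for this, but the variable is to be collected and has no stated place in the model.

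Age raises a similar point. Because the endpoint is at a fixed age, age at entry sets how long an infant can stop before being counted. Taking 3 months as 13 weeks, the upper stratum mixes infants with about 11 weeks still to run (entered at 2 weeks) and infants with about 3 weeks (entered near 10 weeks). A two-level term treats them alike.

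What is at stake is precision. Part of the outcome variance could be explained by data already collected, which would give a narrower interval and slightly more power from the same infants. The covariates are also best fixed before any comparative data are seen.

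**Working it through.** **1. The plan's own figure.** Inputs from section 12.1: 70% versus 80%, 90% power, 5% significance; two-sided from section 12.3. With the pooled-variance formula and mean rate 0.75:

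n = [1.960 × √(2 × 0.75 × 0.25) + 1.282 × √(0.70 × 0.30 + 0.80 × 0.20)]² / 0.10² = 391.9, so 392 per arm and 784 in total.

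This matches the protocol. No covariate enters the calculation, so leaving covariates out creates no shortfall against it.

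**2. Adding feeding status at entry.** Assumptions, none of them in the protocol: half the infants are exclusively breastmilk-fed at entry, and continuation differs by d between exclusive and mixed feeders. The share of outcome variance explained is

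R² = d² × 0.5 × 0.5 / (0.75 × 0.25).

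As an approximation, adjustment multiplies the variance by (1 − R²), so 392 per arm acts like 392 / (1 − R²).

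| Gap d | R² | Effective n per arm | Power |
|---|---|---|---|
| none | 0 | 392 | 90.0% |
| 10 points | 1.3% | 397 | 90.4% |
| 20 points | 5.3% | 414 | 91.5% |
| 30 points | 12.0% | 445 | 93.3% |

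**3. Age as continuous rather than two-level.** Assumptions: a constant stopping hazard h from entry to 13 weeks, so continuation is exp(−h × (13 − age)), with 75% continuing overall.

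- Entry ages uniform over 0 to 10 weeks: h = 0.0367 per week. Expected continuation inside the upper stratum runs from exp(−0.0367 × 11) = 67% to exp(−0.0367 × 3) = 90%. Age explains 3.4% of outcome variance when continuous and 1.5% when split at two weeks. The extra 1.9% takes power from 90.0% to about 90.5%.
- Entry ages skewed young (exponential, mean 3 weeks, cut off at 10): 1.3% against 0.7%. The extra 0.6% gives about 90.2%.

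The uniform case is generous. It puts 60% of infants at four weeks or older, while the internal pilot (section 7.1) works on fewer than 40%. The skewed case puts 24% there.

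**4. Continuous outcomes with a baseline value.** With baseline–outcome correlation ρ (assumed), the variance of the treatment difference is proportional to 1 for follow-up only, 2(1 − ρ) for a change score, and 1 − ρ² for analysis of covariance.

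| ρ | Covariance vs follow-up only | Covariance vs change score |
|---|---|---|
| 0.3 | 0.91 | 0.65 |
| 0.5 | 0.75 | 0.75 |
| 0.7 | 0.51 | 0.85 |

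At ρ = 0.5 the variance is 25% lower than with either alternative. With 392 per arm, the difference detectable at 90% power falls from (1.960 + 1.282) × √(2/392) = 0.232 SD to 0.232 × √0.75 = 0.201 SD.

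**The case against.** The strongest reply is that nothing here is wrong. Adjusting for the stratification factors is sound, the sample size holds without further covariates, and the remaining detail is left to a statistical analysis plan. The gain is a few power points at most and rests on figures that the protocol does not supply. All of that stands, and it sets the weight of the point. It does not remove the point, because the primary covariate list is a choice that the protocol itself states, and a plan that follows section 12.2 as written would have no reason to add feeding status.

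Several stronger readings are tempting but not supported:

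- **That secondary outcomes will be compared by raw differences.** Section 12.2 names effect measures. An adjusted mean difference is still a mean difference, and covariates for secondary outcomes can properly be settled in the analysis plan.
- **That the protocol commits the model to two-level age.** The cut is stated for randomisation and for a subgroup. The model term is simply age at randomisation. Two-level entry is a fair inference from the reference to stratification factors, but it is not stated.
- **That further covariates are ruled out.** The text lists three factors and does not say that there are no others.
- **That baseline weight goes unused.** It defines the post-randomisation weight-gain outcome. That definition does not prevent adjustment either: regressing the change on baseline gives the same treatment estimate as regressing the final value on baseline.
- **That chance imbalance in feeding status or age biases the result.** Randomisation keeps the estimate unbiased, and the confidence interval already allows for chance imbalance. The loss is one of precision.

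**Conclusion.** The point holds as an efficiency suggestion. Section 12.2 names a valid adjustment set that leaves out a plausibly prognostic baseline variable the trial collects, and the only coding offered for age as a stratification factor is coarse for an entry window of 10 weeks.

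For the primary outcome the benefit is small: about 1% to 12% less variance and 0.4 to 3.3 points of power, if half the infants are exclusively breastmilk-fed at entry and the continuation gap is 10 to 30 points. Continuous age alone adds about 0.2 to 0.5 points under a constant hazard. The two gains may overlap and should not simply be added. For continuous secondary outcomes the benefit could be larger (25% less variance at a correlation of 0.5), but the analysis plan may already provide for it. The direction is dependable; the size depends wholly on the assumed gap, hazard and correlation.

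**What to change.** Replace the adjustment sentence in section 12.2 with wording such as:

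> *The primary risk ratio will be adjusted for centre, parity, age at randomisation (continuous) and exclusive breastmilk feeding at baseline. The model with the stratification factors alone will be presented as a sensitivity analysis. Where an outcome has a baseline value (pain, EQ-5D-5L, exclusive feeding, weight-for-age z-score), its comparison will be adjusted for that value.*

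Carry the same text into the statistical analysis plan before any comparative data are seen. The feeding status used should be the one recorded before allocation, since Appendix A lets baseline data be taken at the intervention visit, where randomisation also falls. A modified Poisson model with robust standard errors would give the adjusted risk ratio.

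The cost is a short amendment to section 12.2 and a matching entry in the analysis plan. No new data are needed, the sample size is unchanged, and the sensitivity analysis keeps the current model in view.

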12. STATISTICS AND ANALYSIS

12.1. Sample size

Frenotomy rates are very variable between hospitals (<1% to 6% of babies born) and evidence on which to base an estimate of effect size is very limited. The 2010 Infant Feeding Survey indicates that 68% of infants are breastfed at 6 weeks (McAndrew, Thompson et al. 2010). The current reported rate of any breastfeeding at 6-8 weeks is 4-4% (Public Health England 2016), as compared with 30% exclusive breastfeeding. Breastfeeding rates are likely to be substantially higher in the highly motivated population

eligible for this trial. Breastfeeding rates at 3 months in relatively small studies of UK babies who have undergone frenotomy have varied between 65% in Southampton (Berry, Griffiths et al. 2012) to 78% in London (Khoo, Dabbas et al. 2009). Similarly, in a Bristol trial (Emond, Ingram et al. 2014), breastfeeding rates at 8 weeks were 83% in the intervention arm and 80% in the control arm, noting that most of the control arm underwent frenotomy. Six of eight infants who did not undergo frenotomy were breastfed at 8 weeks (75%). In another Southampton trial (Hogan, Westcott et al. 2005), the breastfeeding rate at 4 months was 60% in both the immediate and delayed division groups. Audit data from the Royal Berkshire Hospital infant feeding service, which includes a frenotomy service, showed that the following proportions of infants referred to the service were exclusively breastfed at three months: 2011/12 66%, 2012/13 62%, 2013/14 61%, 2014/15 77%, 2015/16 69%.

It is assumed, as supported by public consultations, that a 10% increase in the rate of breastfeeding represents the minimal clinically important difference that should be detectable by the trial; and breastfeeding rates will remain high in this motivated population (breastfeeding rates at 3 months will be around 70% in those who receive the minimum level of breastfeeding support).

Thus assuming a breastfeeding rate of 70% in the control group and 80% in the intervention group, at 90% power with a 5% level of significance, this gives a sample size of 392 in each group, totalling 784. Allowing for 5% loss to follow-up, with a further 5% increase to account for between-group contamination would give a sample size of 870; approximately 37 infants per month over a 24 month recruitment period.

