12.3. Level of statistical significance

Two-sided statistical testing will be performed throughout. A 5% level of statistical significance will be used for analyses of all outcomes.

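### Protocol 12.2's mean-or-median rule suits age at last breastmilk poorly, because about 75% of infants are expected to be still breastfed, and so censored, when it is collected at 3 months

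*Protocol*

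**What the plan says.** Protocol section 12.2 gives one estimator rule for each of two outcome types: "Binary outcomes will be analysed using risk ratios, whilst continuous outcomes will be analysed using either a mean or median difference as appropriate". The closing qualifier chooses only between a mean and a median. The same section summarises continuous variables that are not normally distributed by medians, and it commits to comparing all infants as allocated.

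Section 6 lists, as a secondary outcome at 3 months, "age when child last received breastmilk, to determine when and whether switch to exclusive formula feeding has occurred". Section 9.6.3 collects it in the 3-month maternal questionnaire. At 6 months, section 9.6.4 lists only whether the infant is receiving any breastmilk, so a stopping age after 3 months is not among the planned data.

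Section 12.1 sizes the trial "assuming a breastfeeding rate of 70% in the control group and 80% in the intervention group", both rates being at 3 months. The protocol gives no censoring rule, no time-to-event method and no value to enter for an infant who is still breastfed when the question is asked.

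**The concern.** The outcome is meant to show both whether and when breastmilk feeding ended. For most infants the answer at 3 months is that it has not ended, so the observation is right-censored. A rule written for fully observed continuous measurements does not say what to do with these infants, and the natural ways of applying it are not equally good. Two of them would hide or distort a real effect: a median with ages capped at 3 months, and a mean among infants who stopped. A strongly non-normal variable with most values at one ceiling also points, under the protocol's own summary convention, towards the median.

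At stake is the one outcome that describes the timing of stopping. It could be reported as showing no difference in the same paper in which the primary outcome shows the full target benefit.

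**Working it through.** **Inputs from the protocol**
- Still breastfed at 3 months: 70% control, 80% intervention (12.1).
- Power and significance level: "at 90% power with a 5% level of significance" (12.1); "Two-sided statistical testing will be performed throughout" (12.3).
- Allocation 1:1 (9.4).
- Size before inflation: "this gives a sample size of 392 in each group, totalling 784" (12.1).

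**Step 1: reproduce the stated sample size.** Two proportions, pooled variance under the null, no continuity correction:

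n = [1.960 × √(2 × 0.75 × 0.25) + 1.282 × √(0.70 × 0.30 + 0.80 × 0.20)]² / 0.10² = (1.200 + 0.780)² / 0.01 ≈ 392 per group.

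This matches the protocol, so 70% and 80% are the working design rates.

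**Step 2: share censored**
- Control: 0.70 × 392 = 274 still breastfed, about 118 stopped.
- Intervention: 0.80 × 392 = 314 still breastfed, about 78 stopped.
- Total: (274 + 314) / 784 = 588 / 784 = 75% censored; 118 + 78 = 196 observed stopping ages.

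**Step 3: median with ages capped at 3 months.** More than half of each arm sits at the cap, so each median is the cap and the difference is exactly 0. This needs no assumption about when the others stopped. It would change only if fewer than half of an arm were still breastfed.

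**Step 4: the two means.** These depend on stopping patterns, which the protocol does not give, so they are illustrated by simulation. Assumptions: 392 per arm; 3 months taken as 13 weeks; entry at age 2 weeks, or uniform between 0.5 and 10 weeks; Weibull stopping times with shape 0.6, 1 or 1.5, set to give 70% and 80% still breastfed at 13 weeks; 1,500 runs per scenario. Differences are intervention minus control, in weeks. Rejection is at two-sided 5%.

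| Shape | Entry | Mean difference, stopped only | Rejection | Mean difference, all infants capped | Rejection | Median difference, capped |
|---|---|---|---|---|---|---|
| 0.6 | 2 weeks | 0.11 | 6.3% | 0.75 | 86.4% | 0 |
| 0.6 | uniform | 0.09 | 5.3% | 0.53 | 80.3% | 0 |
| 1 | 2 weeks | 0.13 | 6.5% | 0.61 | 81.6% | 0 |
| 1 | uniform | 0.08 | 5.3% | 0.42 | 75.0% | 0 |
| 1.5 | 2 weeks | 0.12 | 6.2% | 0.49 | 79.4% | 0 |
| 1.5 | uniform | 0.08 | 6.2% | 0.35 | 72.2% | 0 |

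The stopped-only mean rejects at little more than the null rate of 5% despite a true 10-point effect. It also compares about 118 with 78 infants who are defined by the primary outcome. The capped mean over all infants recovers the effect.

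**Step 5: what a time-to-event analysis would offer.** Under proportional hazards the design rates imply a hazard ratio of ln(0.80) / ln(0.70) = 0.63. With 196 events, Schoenfeld's formula gives z = |ln 0.6256| × √(196/4) − 1.960 = 0.469 × 7 − 1.960 = 1.32, a power of about 91%.

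**The case against.** The strongest reply has three parts.

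*This belongs in the SAP.* Section 12.2 defers to a pre-specified SAP, which is not at hand and may already set a time-to-event analysis. The quoted sentence is a general default; it neither names this outcome as continuous nor rules out other methods. This stands in part, and it limits the point to a mismatch between a stated rule and one named outcome. The rule is nevertheless written, an age is naturally read as continuous, and a time-to-event SAP would need 12.2 aligned with it.

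*One permitted estimator works.* A reader might infer that the rule fails altogether and would show no effect. The documents do not support that. A mean difference is allowed, and the mean of all ages capped at 3 months is a valid restricted mean if follow-up to that age is complete. Nothing in the protocol restricts the outcome to infants who stopped, and the commitment to compare all infants as allocated points the other way. This stands. What remains is that the protocol does not select that version over the uninformative ones.

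*Other feeding outcomes.* A reader might extend the point to 3-month pain while feeding and to "time in minutes/hours spent breastfeeding in previous 24 hours". That is not supported. Pain is also compared at the first follow-up visit, time spent is naturally 0 for an infant who has stopped, and no text limits either outcome to mothers still breastfeeding.

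**Conclusion.** The point holds as a poor fit between the general rule in 12.2 and one secondary outcome. The 75% censored and the zero capped-median difference follow directly from the protocol's own 70% and 80%. The sizes of the two mean differences rest on assumed entry ages and stopping patterns and are illustrations only. The hazard ratio of 0.63 and power of about 91% assume proportional hazards and 392 infants per arm with outcome data. The primary analysis and the sample size are not affected. The matter is worth correcting before analysis, because choosing among these versions after seeing the data could decide whether an effect on timing is reported.

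**What to change.** In section 12.2, and in the SAP if it does not already do so, exempt age at last breastmilk from the mean-or-median rule. State that it is analysed in all randomised infants as time from randomisation to last breastmilk, with infants still breastfed censored at 3 months of age or at last contact if earlier. Report Kaplan-Meier curves by arm and either a hazard ratio or a restricted mean difference, adjusted for centre, infant's age at randomisation and mother's parity. Name one of the two as the main estimate and, if it is the restricted mean, state its horizon, since infants enter at different ages.

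The cost is one paragraph. The 3-month questionnaire already asks for the age, so no new data collection and no change to the sample size are needed.
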